Title of the study: Rehabilitative Trial With Cerebello-Spinal tDCS in Neurodegenerative Ataxia

NCT number: NCT03120013

Date: January 21, 2016

Standard Protocol Approvals, Registrations, and Patient Consents

Full written informed consent was obtained from all participants according to the Declaration of Helsinki. The study protocol was approved by the local ethics committee (Brescia Hospital), #NP1576 approved 01.21.16. This trial has been registered at ClinicalTrials.gov (NCT03120013).

Primary research questions/classification of evidence

Our primary research question was to determine whether cerebellar anodal tDCS and spinal cathodal tDCS could improve symptoms and modulate cerebello-cerebral connectivity in patients with ataxia, at short and long-term.

Participants

Twenty-one patients with neurodegenerative ataxia, respectively seven patients with spinocerebellar ataxia (SCA) type 2,¹ six with the cerebellar variant of multiple system atrophy (MSA-C),² one with SCA38,³ one with SCA14,⁴ one with Friedreich's ataxia,⁵ one with Ataxia with Oculomotor Apraxia (AOA) type 2,⁶ four with sporadic adult-onset ataxia,⁷ were recruited from the Centre for Ageing Brain and Neurodegenerative Disorders, Neurology Unit, University of Brescia, Italy and entered the study. One patient with MSA-C dropped out from the study during the first round (sham stimulation) and was not considered in the present analysis.

The number of included patients, corrected for possible drop-outs and patients in which a reliable motor cortex could not be elicited, was assessed using a power analysis, from results obtained from previous studies.⁸

Each patient fulfilled current clinical criteria and genetic trait for the specific diagnosis. All enrolled patients shared a cerebellar syndrome and, as assessed by MRI, had quantifiable cerebellar atrophy. For each patient, a review of past medical history, a semi-structured neurological examination and a standardized assessment of cerebellar functions was carried out.

Patients were evaluated free of sedative drugs or sodium- or calcium-channel blockers to avoid any interaction with the presumed neuromodulatory effects of tDCS.

In addition, ten age-matched healthy control subjects were recruited as reference group for TMS parameters.

Study design

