Patients were randomized into two groups: each group received anodal cerebellar tDCS and cathodal spinal tDCS (real tDCS) or sham stimulation for 5 days/week for 2 weeks, in a 1:1 ratio respectively.

At baseline, each patient underwent a clinical evaluation, according to a standardized assessment (see below, clinical assessment), and CBI evaluation using Transcranial Magnetic Stimulation (TMS) (see below, CBI assessment) (pre-stimulation, T0). The same assessments were carried out after two-weeks of either real or sham tDCS (post-stimulation, T1), at one-month (T2) and at three-months follow-up (T3).

After a wash-out period of three months after the last visit (i.e., T3), each patient received the opposite treatment (cross-over phase), and underwent the same standarized assessment as in the first phase, at baseline, at two-weeks post-stimulation, at one-month and at three-months (see **Fig 1**).

Six principal investigators were involved: one performing the clinical evaluation ([name]), one performing CBI at baseline and at follow-up ([name]) and four performing tDCS ([name], [name], [name], [name]). The patient and the examiners performing clinical ratings and TMS protocols were blinded to the type of stimulation.

Clinical assessment

At each time-point, the Scale for the Assessment and Rating of Ataxia (SARA)⁹ and the International Cooperative Ataxia Rating Scale (ICARS)¹⁰ were employed to evaluate cerebellar deficits.

SARA consists of eight items, including gait, stance, sitting, speech disturbance, finger chase, nose-finger test, fast alternating hand movements, and heel-shin slide. The higher the score, the worse is the patient's performance. ICARS is a semiquantitative 100-point scale consisting of 19 items, divided into four weighted sub-scores, namely posture and gait disturbances, limb kinetic function, speech disorder, and oculomotor deficits.

To evaluate finger dexterity and upper limb coordination, four timed trials of the 9-hole peg test (9HPT)¹¹ were performed separately for each hand. The 9HPT is a commonly used test to assess finger dexterity: the patient picks the pegs one at time and puts them in nine holes on a peg board until all holes are filled and then removes them one at a time, as quickly as possible. The total time to complete the task is recorded for each trial and for each separate hand (dominant and non-dominant).

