To assess the effect of tDCS treatment on clinical scores over time we used a two-way repeated measure ANCOVA with TIME (T0, T1, T2 and T3) and TREATMENT (sham vs real stimulation) as within-subjects factors, and the sequence in which stimulation was performed (real-sham vs sham-real) as covariate.

To assess the effect of tDCS treatment on CBI we used a three-way repeated measures ANCOVA with TIME (T0, T1, T2 and T3), ISI (3, 5, 10 ms) and TREATMENT (sham vs real stimulation) as within-subject factors, and the sequence in which stimulation was performed (real-sham vs sham-real) as covariate.

When a significant main effect was reached, *post hoc* tests with Bonferroni correction for multiple comparisons were conducted to analyze group-differences at respective ISIs or time points. Mauchly's test was used to test for assumption of sphericity, while Greenhouse–Geisser epsilon determination was used to correct in case of sphericity violation.

Spearman's rank-order correlations were used to assess associations between the improvement in functional scores, neurophysiological parameters and demographic or clinical characteristics. Statistical analyses were performed using SPSS version 21 (SPSS, Inc., Chicago, IL, USA).

References

6. Moreira M-C, Klur S, Watanabe M, et al. Senataxin, the ortholog of a yeast RNA helicase, is mutant in ataxia-ocular apraxia 2. *Nat Genet*. 2004;36(3):225-227. doi:10.1038/ng1303.

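### The Spearman correlations between clinical change and CBI change omit the sequence adjustment used in both ANCOVAs, so large phase differences in both measures could bias them (minor)

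*Combined protocol and SAP*

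**What the plan says.** In the combined protocol and SAP, Statistical Analyses, the ANCOVA for clinical scores and the ANCOVA for CBI each include "the sequence in which stimulation was performed (real-sham vs sham-real) as covariate". The correlation sentence in the same section states that Spearman's "rank-order correlations were used to assess associations between the improvement in functional scores, neurophysiological parameters and demographic or clinical characteristics". It gives no partial or stratified version, and no other section adds one. It also does not say which phase, time point or interstimulus interval supplies the change scores, or whether they come from the real phase alone or are real minus sham.

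Under Study design, patients are randomised "in a 1:1 ratio respectively" to the order of stimulation, and the second phase is described as follows: "After a wash-out period of three months after the last visit (i.e., T3), each patient received the opposite treatment". Under Participants, the sample is "Twenty-one patients with neurodegenerative ataxia", and "One patient with MSA-C dropped out from the study during the first round (sham stimulation) and was not considered in the present analysis".

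**The concern.** About half of the patients receive real stimulation in phase 1. The rest receive it about six months later (three months to T3, then three months of wash-out), after four previous assessment rounds with repeated timed tests and after experiencing the other condition. Suppose the amount of change depends on the phase. The two sequence groups then have different mean change scores. If that happens for both the clinical score and CBI, a pooled rank correlation counts the difference between groups as part of the association between patients. Gaps in the direction of the expected association can create or inflate a correlation. Gaps against it can hide one.

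The plan allows for order when it compares means but not when it correlates changes. With 20 patients, a misleading coefficient could be read as support for a mechanism, or its absence as evidence against one.

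**Working it through.** **Inputs from the documents.** The diagnosis counts give 7 + 6 + 1 + 1 + 1 + 1 + 4 = 21 enrolled. One dropout leaves 20 analysed. The plan states no figure for the correlations. The sample size "was assessed using a power analysis, from results obtained from previous studies", but without alpha, power, effect size or SD it cannot be reproduced.

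**Assumptions.**
- The correlated quantities are clinical change and CBI change. The text says only neurophysiological parameters, but CBI is the neurophysiological outcome measured at every visit.
- The sequence split of the 20 is 10/10. The dropout was in a sham first round, so 21 randomised as 10 real-first and 11 sham-first leaves 10/10, and 11 and 10 leaves 11/9.
- Tests are two-sided at 5%, and the data are normal within sequence.
- The gap d between sequence groups, in within-sequence SD, is unknown. It is varied here, mainly over 0 to 1.0.

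**Expected coefficient.** With a fraction p of patients in one sequence, a gap d adds p(1 − p)d² to the variance, which is d²/4 at 10/10. For gaps dx and dy and within-sequence correlation ρ, the pooled Pearson coefficient is about

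(ρ + dx·dy/4) / √[(1 + dx²/4)(1 + dy²/4)].

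- ρ = 0, equal gaps: 0.5 SD gives 0.0625/1.0625 = 0.059; 0.7 SD gives 0.1225/1.1225 = 0.109; 1.0 SD gives 0.25/1.25 = 0.200.
- ρ = 0.5, opposite gaps: 0.5 SD gives 0.4375/1.0625 = 0.412; 0.7 SD gives 0.3775/1.1225 = 0.336; 1.0 SD gives 0.25/1.25 = 0.200.
- ρ = 0, gaps of 1.0 and 0.3 SD: 0.075/√(1.25 × 1.0225) = 0.066.
- ρ = 0, a gap in one variable only: 0.
- 11/9 split: p(1 − p) = 0.55 × 0.45 = 0.2475 in place of 0.25, so the 1.0 SD case gives 0.2475/1.2475 = 0.198.

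**Simulation.** Each scenario used 40,000 trials. Plain Spearman was tested by t on 18 df. The adjusted version centres the ranks within sequence and tests on 17 df. Ranges show the spread over repeated runs.

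| Gap in both variables (SD) | False positives, same direction: plain | adjusted | Power at ρ = 0.5, opposite directions: plain | adjusted |
|---|---|---|---|---|
| 0 | 5.0% | 5.1% | 57% | 54–55% |
| 0.5 | 5.6–5.8% | about 5% | 39% | 54% |
| 0.7 | 7.1–7.6% | about 5% | 25% | 53–54% |
| 1.0 | 13.9–14.2% | about 5% | 9% | 52–53% |

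Further results:
- Same-direction gaps of 1.0 SD with ρ = 0.5 raise the mean plain Spearman coefficient from 0.46 to 0.57.
- A 1.0 SD gap in one variable leaves the false-positive rate at 5.1%. Gaps of 0.5, 0.7 and 1.0 SD in one variable reduce power to 54%, 51% and 46%.
- Unequal same-direction gaps of 1.0 SD in the clinical score and 0.2 or 0.3 SD in CBI give 5.5% and 5.8–5.9% false positives.
- With an 11/9 split, results stay within 1 point.

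**Real-minus-sham scores.** A phase difference δ enters with opposite signs in the two sequences, so the gap is 2δ. If the two phase changes are independent with equal SD, the SD of their difference is 1.41 times as large, and the standardised gap is 2δ/1.41. Thus δ = 0.5 gives 0.71 and δ = 0.7 gives 0.99. The issue remains under either definition of improvement.

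**The case against.** The strongest reply is that the decisive input is missing: no section reports a phase effect for any outcome. The suggested mechanisms are also weak for CBI. Practice is plausible for the peg test and the walk, but CBI is a ratio of motor responses recorded at rest, which is not a practised task. Steady progression shifts levels, not change scores: it leaves no gap in a one-phase change and cancels in real minus sham. Patients and raters were blinded, which limits expectation. Nothing explains why clinical change and CBI change should shift in opposite directions, which is the case with the largest loss. All of this stands. It limits how likely and how large the bias is, but it does not show that the bias is absent.

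A reader might go further and infer any of three things that the documents do not support.
- *The primary question depends on these correlations.* It asks whether stimulation improves symptoms and whether it modulates connectivity. Those are two treatment effects, each tested by an ANCOVA that includes sequence.
- *Correlations with age or other baseline traits may be false for the same reason.* Sequence is randomised, so such traits have no systematic sequence gap. Only some power is lost.
- *A correlation found by the plain method is an artefact.* That would need sizeable gaps in both change scores, and no figure for either is given.

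**Conclusion.** The point holds as a minor one. The plan adjusts for sequence in its mean comparisons and not in its correlations, and the omission can bias the coefficient between clinical change and CBI change when both differ between phases. Creation of false associations is small below a gap of about 0.7 SD in both measures, is material near 1.0 SD, and is close to nil when only one measure shifts. Masking is the larger risk: it is already appreciable at opposite gaps of 0.5 SD, although no mechanism for opposite gaps is documented. The conclusion rests on assumed gap sizes and on reading the correlated quantities as clinical and CBI change scores. It depends little on whether the split is 10/10 or 11/9.

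**What to change.** In Statistical Analyses, state that correlations between clinical change and CBI change are partial Spearman correlations adjusted for sequence (real-sham vs sham-real): rank both variables over all analysed patients, subtract the mean rank of each sequence group, correlate the residuals, and test on n − 3 = 20 − 3 = 17 degrees of freedom. The same sentence should name the change scores used. For correlations with baseline demographic or clinical characteristics the adjustment is optional and only recovers some power.

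The cost is one sentence, no new data and one degree of freedom. The critical coefficient rises from 0.444 to 0.456, and power at a true correlation of 0.5 falls by about 2 points (57% to 54–55%) if the phases do not differ. In return, the false-positive rate stays at 4.9–5.2% for every gap tested from 0 to 2 SD.
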